### **5.8.2. Data Monitoring Committee (DMC) Review**

An IDMC will be established to monitor data on an ongoing basis to ensure the continuing safety of the participants enrolled in this study and to meet efficacy objectives. This committee will consist of at least one medical expert in the relevant therapeutic area, at least one medical expert in cardiology, and at least one statistician; committee membership responsibilities, authorities, and procedures will be documented in its charter. The committee will meet periodically to review safety and efficacy data and results. After the review of the interim (futility) analysis results at Week 24, the IDMC will make recommendations regarding the continuation of the study.

## 6. SUPPORTING DOCUMENTATION

### 6.1. Appendix 1 List of Abbreviations

AE	adverse event
ALT/SGPT	alanine aminotransferase
AST/SGOT	aspartate aminotransferase
ATC	anatomic and therapeutic class
AUC	area under the curve
BDQ	Bedaquiline
CAM	Clarithromycin
CI	confidence interval
C max	maximum concentration
CRF	case report form
CV	coefficient of variation
DMC	Data Monitoring Committee
DMID	division of microbiology and infectious diseases
EB	Ethambutol
ECG	electrocardiogram
eCRF	electronic case report form
F (%)	absolute SC bioavailability
FU	follow-up
IQ	interquartile
MAC-LD	mycobacterium avium complex-lung disease
MedDRA	Medical Dictionary for Regulatory Activities
PD	pharmacodynamic(s)
PK	pharmacokinetic(s)
SAE	serious adverse event
SAP	statistical analysis plan
SD	standard deviation
SMQs	standardised MedDRA queries
SOC	standard of care
TEAE	treatment-emergent adverse event
WHO	World Health Organization
WHO-DD	World Health Organization Drug Dictionary

## **6.2. Appendix 2 Changes to Protocol-Planned Analyses**

The per-protocol analysis set defined in the protocol will not be used for analysis.

### 6.3. Appendix 3 Demographics and Baseline Characteristics

Tabulations of demographic and baseline characteristics will be presented by intervention arm and overall for the ITT analysis set. Continuous variables will be summarized by descriptive statistics including the number of participants, mean, standard deviation, median, range and interquartile range. Categorical/binary variables will be summarized by counts and percentages.

Table 7 and Table 8 present demographic variables and baseline characteristics that will be summarized by intervention group and overall for the ITT analysis set.

**Table 7: Demographic Variables**

Continuous Variables:	Summary Type
Age ([years])	Descriptive statistics (N, mean, standard deviation [SD], median and range [minimum and maximum], and IQ range).
Weight (kg)	
Height (cm)	
Categorical Variables	
Age (<60 years, ≥60 to <70 years and ≥70 years)	Frequency distribution with the number and percentage of participants in each category.
Sex (male, female, undifferentiated)	
Region [Japan, non-Japan]	

**Table 8: Baseline characteristics**

Continuous Variables:	Summary Type
Duration of previous therapy for MAC-LD (yr) ([years])	Descriptive statistics (N, mean, standard deviation [SD], median and range [minimum and maximum], and IQ range).
Categorical Variables	
MAC species (M.avium, M.intracellulare, M.avium+M.intracellulare)	Frequency distribution with the number and percentage of participants in each category.
Previous therapy for MAC-LD (CAM, AZM, EB...)	
Number of previous therapies for MAC-LD (1, 2, 3, 4, ≥5)	
Duration of previous therapy for MAC-LD (<24 months, ≥24 to <36 months, ≥36 months)	

#### **6.4. Appendix 4 Protocol Deviations**

Only major protocol deviations will be summarized. Protocol deviations and violations will be based on clinical review, but not limit to. Participants with major protocol deviations will be identified prior to database lock and the participants with major protocol deviations will be summarized by category.

- Entered but did not satisfy inclusion/exclusion criteria
- Received an excluded concomitant treatment
- Efficacy assessment deviation
- Received wrong treatment or incorrect dose
- Other

All major protocol deviations will be tabulated by coded term by intervention arm for the ITT analysis set. A listing of the major protocol deviations will also be presented.

## **6.5. Appendix 5 Prior and Concomitant Medications**

Prior and Concomitant medications will be coded using the World Health Organization Drug Dictionary (WHO-DD). Prior medications are defined as any therapy used before the day of first dose (partial or complete) of study intervention. Concomitant medications are defined as any therapy used on or after the same day as the first dose of study intervention, including those that started before and continue on after the first dose of study intervention. Medication that started before Day 1 and continued afterwards will be summarized both as prior and, separately, as concomitant medication.

Summaries of prior and concomitant medications will be presented by ATC term and preferred term by intervention group. The proportion of participants who receive each concomitant medication will be summarized by analysis phase as well as the proportion of participants who receive at least 1 concomitant medication.

## **6.6. Appendix 6 Medical History**

A tabulation of the general medical history coded terms will be provided by body system class and by intervention arm.

**6.7. Appendix 7 Intervention Compliance**

Compliance will be summarized descriptively for each study intervention. Compliance to randomized intervention versus actual intervention will be presented in a summary table.

The average of percentage of treatment compliance will be summarized by intervention group in the investigation phase and the optional investigation phase.

Compliance will be calculated as follows:

Compliance (%) =  $100 \times \text{number of days taking study intervention} / \text{number of days of planned study intervention intake}$

Subjects with 80% or more compliance will be considered compliers.

**6.8. Appendix 8 Adverse Events of Special Interest**

Adverse events of special interest are defined using SMQ (MedDRA version 27.1) as follows:

- Acute pancreatitis (narrow and broad B terms)
- Rhabdomyolysis/myopathy (narrow A terms)
- Severe cutaneous adverse events (narrow and broad terms)
- Torsade de pointes/QT prolongation (narrow and broad terms)
- Hepatic disorders (selected sub-SMQs) shows:
  - All narrow and broad terms of Cholestasis and jaundice of hepatic origin SMQ
  - All narrow terms of Hepatic failure, fibrosis and cirrhosis and other liver damage-related conditions SMQ
  - All narrow terms of Hepatitis, noninfectious SMQ
  - All narrow terms of Liver related investigations, signs and symptoms SMQ
  - All narrow terms of Liver-related coagulation and bleeding disturbances SMQ

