### 8.3.7. Adverse Events of Special Interest

The liver, skeletal muscle, heart, pancreas, and stomach have been identified as target organs in nonclinical toxicology studies. Careful monitoring of these organs should be included in clinical studies. Any abnormalities in the parameters related to these target organs are therefore considered as AEs of special interest. Because other compounds for treatment of MAC, with which BDQ will have to be administered, have been associated with rash, skin events are considered as AEs of special interest as well in the study.

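### The SAP's list of adverse events of special interest has no gastric category and only a severe-reaction search for skin, so its summary does not cover the groups the protocol defines

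*SAP*

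**What the plan says.** Protocol 8.3.7 sets the definition. It states that "The liver, skeletal muscle, heart, pancreas, and stomach have been identified as target organs in nonclinical toxicology studies", and follows with a wide rule: "Any abnormalities in the parameters related to these target organs are therefore considered as AEs of special interest". It then adds a sixth group on different grounds. The other MAC drugs given with bedaquiline "have been associated with rash", and so "skin events are considered as AEs of special interest as well in the study". Neither rule carries a severity threshold.

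SAP 5.6.2 plans an incidence summary of treatment-emergent AESI by intervention group and analysis phase, and sends the reader to Appendix 8 for the events in each category. Appendix 8 opens: "Adverse events of special interest are defined using SMQ (MedDRA version 27.1) as follows". Five searches make up the list:

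- for the pancreas, "Acute pancreatitis (narrow and broad B terms";
- for the liver, five selected hepatic sub-searches;
- for skeletal muscle, a rhabdomyolysis/myopathy search limited to narrow A terms;
- for the heart, a torsade and QT search that uses both narrow and broad terms;
- for the skin, only "Severe cutaneous adverse events (narrow and broad terms".

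SAP Appendix 2, on changes from the protocol's planned analyses, has one entry: "The per-protocol analysis set defined in the protocol will not be used for analysis".

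**The concern.** An AESI summary gives one count per pre-specified group: how many participants in each arm had any event of that kind. If the list behind it leaves out a group that the protocol names, that count is never produced, and nothing in the table shows that it is missing.

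The two affected groups bear on the randomised contrast. Protocol 2.2.1 lists gastrointestinal disorders and rash among the frequent events with rifampicin, the usual comparator. Protocol 2.3 lists nausea and vomiting as very common with bedaquiline. Protocol 8.2.6 gives gastrointestinal toxicity its own paragraph, and Protocol 8.2.1 has the skin observed at scheduled examinations. The data will be collected, but the planned summary has no row for any gastric event and none for skin events in general.

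**Working it through.** No sample size, error rate or event rate enters, so the check is a mapping from one list to the other.

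| Group in Protocol 8.3.7 | Search in SAP Appendix 8 | Match |
|---|---|---|
| Liver | Hepatic disorders, five sub-searches | Yes |
| Skeletal muscle | Rhabdomyolysis/myopathy, narrow A terms | Yes |
| Pancreas | Acute pancreatitis, narrow and broad B terms | Yes |
| Heart | Torsade/QT, narrow and broad terms | Narrower label |
| Skin events | Severe cutaneous, narrow and broad terms | Narrower label |
| Stomach | None | None |

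The count is 3 matched + 2 with a narrower label + 1 unmatched = 6 protocol groups, against 5 SAP searches. The term choice within matched groups is also restrictive in places: muscle uses narrow A terms only, and four of the five hepatic sub-searches use narrow terms only. Those rows still address the organ that the protocol names, so I count them as matched.

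**Stomach.** No search in Appendix 8 has a gastric or gastrointestinal label. I looked for another route. SAP 5.6.3.1 summarises laboratory values and toxicity grades, and SAP 5.6.3.3 summarises ECG data. Between them they reach liver enzymes, amylase and QTc. The test list in Protocol Appendix 2 has transaminases for liver, creatine phosphokinase for muscle, its MB fraction for heart muscle and amylase for pancreas, but no test specific to the stomach. Adverse-event terms are therefore the main way gastric toxicity can show in the outputs, and this is the organ with no AESI search.

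**Skin.** The protocol's reason for the group is rash. The SAP's search is built around severe reactions. Its broad terms may take in some milder skin terms, but neither document lists the contents of the search. What can be said is that capture of ordinary rash is not assured. How many such events would be missed cannot be determined.

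**Heart.** The protocol names the organ without listing event types, and 8.2.6 treats rhythm disturbances as a category of their own. The SAP search is labelled torsade/QT. Whether its broad terms reach other rhythm events cannot be read from the documents.

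**Other tables.** SAP 5.6.2 also tabulates all treatment-emergent events, and breaks them down by seriousness, severity, relationship, discontinuation, dose interruption or modification, and onset time. Gastric and skin events appear there as individual terms. The section orders rows by descending incidence and does not mention organ grouping. Nothing in it commits to a count of participants with any gastric event or any skin event.

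**The case against.** Four points can fairly be made for the SAP.

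First, the two texts define different things. The protocol speaks of abnormal parameters related to the organs, while the SAP sorts adverse-event terms. Parameter abnormalities are summarised elsewhere: laboratory grades and shifts, ECG intervals, and physical-examination findings in frequency tables. This stands for liver, pancreas and QT, and partly for skin. It does not help the stomach, and the protocol's skin rule is written in terms of events.

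Second, Protocol 9.4.6 plans no AESI analysis, and Protocol 9 leaves analysis detail to the SAP. No planned table was altered, so the silence of SAP Appendix 2 is not in itself an error. This stands. The discrepancy is with the definition in 8.3.7. The SAP uses the protocol's AESI term for a summary whose content differs from that definition, and gives no reason.

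Third, the consequences are limited. SAP 5.6 makes all safety summaries descriptive, so no test changes. Every event is still coded and tabulated, and a grouping can be added at reporting. This stands too, and it keeps the point small.

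Fourth, a reader might infer that the AESI table will show no ordinary rash however many cases occur, or that rhythm events other than QT prolongation lie outside the cardiac search. The documents support neither. Both searches use narrow and broad terms whose contents are not given, and ECG parameters and clinically relevant ECG abnormalities are reported separately under SAP 5.6.3.3.

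**Conclusion.** The point holds for stomach and skin. Appendix 8 as written omits one of the protocol's six AESI groups altogether. For a second, skin, it substitutes a search that does not assure capture of the non-severe events for which the protocol created the group. For heart the documents raise a question that the sponsor can answer, but do not establish a gap.

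The effect is confined to one descriptive summary. Data collection, the general adverse-event tables and the efficacy analysis are untouched. It would be wrong to read this as safety information being lost: what is missing is the grouped count by arm and phase. The conclusion assumes that Appendix 8 is the complete list for the summary, which is how SAP 5.6.2 refers to it. It does not depend on which terms the MedDRA searches contain, except for the amount of rash missed, which I leave unquantified.

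**What to change.** In SAP Appendix 8:

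- Add a gastric category, with the terms or search that define it written out. The documents do not say which events the protocol means by stomach, so the SAP must.
- Add a general skin/rash category, and keep the severe cutaneous search as a subset reported beneath it.
- For heart, check the contents of the torsade/QT search against the protocol's group. Either widen it or state in the SAP why the narrower definition is used.

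Summarise the new categories by intervention group and analysis phase, as SAP 5.6.2 already provides. If the sponsor prefers the present list, the alternative is to record and justify the narrower definition in SAP Appendix 2, so that a reader of the AESI table knows that it does not cover every group in Protocol 8.3.7.

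The cost is a few more searches on events that are coded in MedDRA in any case, and a few more table rows. No new data and no change to trial conduct are needed.

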## **6.9. Appendix 9 Medications of Special Interest**

Not applicable.

**6.10. Appendix 10 Laboratory Toxicity Grading**

The grading scale use for lab assessments is based on DMID and defined as follows.

**Hematology**

	Grade 1	Grade 2	Grade 3	Grade 4
Hemoglobin	9.5 - 10.5 gm/dL	8.0 - 9.4 gm/dL	6.5 - 7.9 gm/dL	<6.5 gm/dL
Absolute Neutrophil Count	1000 - 1500 /mm 	750 - 999 /mm 	500 - 749 /mm 	<500 /mm 
Platelets	75,000 - 99,999 /mm 	50,000 - 74,999 /mm 	20,000 - 49,999 /mm 	<20,000 /mm 
White Blood Cell (WBC) Count	11,000 - 13,000 /mm 	13,000 - 15,000 /mm 	15,000 - 30,000 /mm 	>30,000 or <1,000 /mm 
Prothrombin Time (PT)	1.01 - 1.25 x ULN	1.26 - 1.5 x ULN	1.51 - 3.0 x ULN	>3 x ULN

**Chemistry**

	Grade 1	Grade 2	Grade 3	Grade 4
Hyponatremia	130 - 135 mEq/L	123 - 129 mEq/L	116 - 122 mEq/L	<116 mEq/L
Hypernatremia	146 - 150 mEq/L	151 - 157 mEq/L	158 - 165 mEq/L	>165 mEq/L
Hypokalemia	3.0 - 3.4 mEq/L	2.5 - 2.9 mEq/L	2.0 - 2.4 mEq/L	<2.0 mEq/L
Hyperkalemia	5.6 - 6.0 mEq/L	6.1 - 6.5 mEq/L	6.6 - 7.0 mEq/L	>7.0 mEq/L
Hypoglycemia	55 - 64 mg/dL	40 - 54 mg/dL	30 - 39 mg/dL	<30 mg/dL
Hyperglycemia (nonfasting and no prior diabetes)	116 - 160 mg/dL	161 - 250 mg/dL	251 - 500 mg/dL	>500 mg/dL
Hypocalcemia (corrected for albumin)	8.4 - 7.8 mg/dL	7.7 - 7.0 mg/dL	6.9 - 6.1 mg/dL	<6.1 mg/dL
Hypercalcemia (correct for albumin)	10.6 - 11.5 mg/dL	11.6 - 12.5 mg/dL	12.6 - 13.5 mg/dL	>13.5 mg/dL
Hypomagnesemia	1.4 - 1.2 mEq/L	1.1 - 0.9 mEq/L	0.8 - 0.6 mEq/L	<0.6 mEq/L
Hypophosphatemia	2.0 - 2.4 mg/dL	1.5 - 1.9 mg/dL	1.0 - 1.4 mg/dL	<1.0 mg/dL

	Grade 1	Grade 2	Grade 3	Grade 4
Hyperbilirubinemia (with Grade 1 or more AST, ALT or ALP)	1.1 - <1.25 x ULN	1.25 - <1.5 x ULN	1.5 – 1.75 x ULN	>1.75 x ULN
Hyperbilirubinemia (with normal AST, ALT and ALP)	1.1 - <1.5 x ULN	1.5 - <2.0 x ULN	2.0 - 3.0 x ULN	>3.0 x ULN
Blood urea nitrogen (BUN)	1.25 - 2.5 x ULN	2.6 - 5 x ULN	5.1 - 10 x ULN	>10 x ULN
Hyperuricemia (uric acid)	7.5 - 10.0 mg/dL	10.1 - 12.0 mg/dL	12.1 - 15.0 mg/dL	>15.0 mg/dL
Creatinine	1.1 - 1.5 x ULN	1.6 - 3.0 x ULN	3.1 - 6 x ULN	>6 x ULN
AST (SGOT)	1.1 - <2.0 x ULN	2.0 - <3.0 x ULN	3.0 - 8.0 x ULN	>8 x ULN
ALT (SGPT)	1.1 - <2.0 x ULN	2.0 - <3.0 x ULN	3.0 - 8.0 x ULN	>8 x ULN
GGT	1.1 - <2.0 x ULN	2.0 - <3.0 x ULN	3.0 - 8.0 x ULN	>8 x ULN
Alkaline Phosphatase	1.1 - <2.0 x ULN	2.0 - <3.0 x ULN	3.0 - 8.0 x ULN	>8 x ULN
Amylase	1.1 - 1.5 x ULN	1.6 - 2.0 x ULN	2.1 - 5.0 x ULN	>5.1 x ULN

### Urinalysis

	Grade 1	Grade 2	Grade 3	Grade 4
Proteinuria	1+	2-3+	4+	NA

## 6.11. Appendix 11 Unblinding Plan

This unblinding plan details who will be unblinded to the microbiological result data and the documentation of unblinding until the completion of the primary analysis.

The default unblinders are as follows.

- Site Manager
- Local Trial Manager
- Global Trial Lead (GTL)
- Clinical Trial Manager (CTM)
- Clinical Trial Assistant
- Clinical Research Manager
- Vendor manager for Central lab

Default unblinders are required to give their consent ([Appendix 12](#)) to declare not to disclose any microbiological result data to any non- unblinders to maintain the data integrity of this trial. The GTL/CTM will keep a running log ([Appendix 13](#)) of personnel who have been unblinded to microbiological result data and the date of their consent.

Any sponsor personnel other than the above default unblinders will not have access to microbiological result data after Week 2 until unblinding takes place for the primary analysis except for the investigator's decision related to therapy based on microbiological result (e.g. transfer to optional cohort, individualized treatment regimen, or follow-up period).

## 6.12. Appendix 12 Agreement on the Unblinded Information Handling

**TMC207NTM3002** study is a multicenter, randomized, open-label, active-controlled study. The primary analysis of this study will be carried out after all participants have reached Week 24 or have discontinued earlier than Week 24.

As this is an open-label study, blinding procedures are not applicable. However, the microbiological results from Week 2 to Week 24 will be blinded to the investigators, site staffs and participants until the completion of the other assessments at Week 24 by the investigators. In order to maintain the blind, the investigator should not perform microbiological tests for acid-fast bacillus at the study site after Day 1 until completion of the assessments other than microbiological assessments at the Week 24 except in emergency situations related to subject safety or chemotherapy. In case the investigators need to know the microbiological result to decide if participants should be switched to an individualized treatment regimen or continue the study treatment regimen, due to clinical worsening, the investigators can access the microbiological result from the central laboratory (for the detailed procedure, refer to the Procedure for Confirmation and Reporting of Results of Blinded Sputum Culture Including Collection of Samples for Microbiology Test). Sponsor except for specific personnel listed below must keep the blinding of all the microbiological assessment after Week 2 until unblinding takes place for the primary analysis except for the investigator's decision related to therapy based on microbiological result (e.g. transfer to optional cohort, individualized treatment regimen, or follow-up period).

In addition, sponsor personnel involved in monitoring of the study sites and personnel involved in management operation of the central laboratory etc. are excluded from maintenance of blinding for microbiology assessments, taking into account that sponsor needs to confirm that investigators and etc. comply with the protocol and the decision to switch to individualized treatment regimen and the optional cohort is made based on the appropriate process.

The access to the unblinded microbiology result data will be strictly limited to the default unblinders who have signed this agreement. A list of all default unblinders will be provided by the GTL/CTM. To be a default unblinders of this study, you need to fully understand the above and agree as follows:

- Not sharing any microbiological result data from Week 2 until unblinding takes place for the primary analysis with other than the default unblinders in any manner.
- Not printing any microbiological result data from Week 2 until unblinding takes place for the primary analysis.
- Immediately reporting any potential deviations from this agreement occurred in any default unblinders to the GTL/CTM of this study.
- Immediately reporting to the GTL/CTM of this study if any existing default unblinder is replaced by other responsible personnel.

This agreement shall become effective from the date of its signature and remain valid until the completion of the primary analysis.

I consent to take special care to protect the integrity.

---

(Signature)

